5.1.1.1. Starting Dose and Dose Levels

The prescribed dose will be 90 mcg, 1 to 2 inhalations every 4 to 6 hours, as needed. No dose escalations are planned.

5.1.1.2. Dose Modification and Dose Stratification

Not applicable.

5.1.2. Medical Devices

Instructions for medical device use are provided in the Study Pharmacy Manual.

5.1.2.1. Application

The software App is a customer facing software/focused smart device application for patients using the Albuterol eMDPI Inhalation Powder combination product. The intention of the smart device App is to engage patients with asthma and/or COPD (and their caregivers) by tracking medication usage, raising awareness of medication use patterns, allowing users to self-assess their respiratory symptoms on a daily basis, sharing information on local environmental conditions, and producing user reports to review their data over time.

The software consists of a smart device application compatible for iPhone operating systems (iOS) and Android operating systems that will store data locally on the patient's smart device. The App will receive a patient's inhaler use/event data automatically from the inhaler devices via Bluetooth on a smart device. The smart device camera will be used for scanning and pairing. This data will allow the patient to track their usage of medication, inhalation results, and self-assessments related to their asthma and/or COPD. The App gets environment information for the specific location of the patient.

5.1.2.2. Teva Digital Health Platform (Cloud Solution)

The Teva DHP is a system that stores and transfers inhaler use/event data collected from the App. The Cloud solution automatically synchronizes with the App after events and/or at predetermined time periods/intervals. An internet connection to the smart device (eg, wireless or cellular phone network) is required in order for communication to be established between the App and the Cloud solution. The Cloud solution will not send any notifications to the App. The Cloud solution does not create, modify, or delete patient information.

Patient privacy will be maintained according to the laws and regulations, and patient identifiers will be substituted to maintain a patient's privacy to reviewers of the data.

5.1.2.3. Dashboard

The DHP may be used to provide patient-specific data to the iHCP via the dashboard, a secure web interface. The data available on the dashboard are the inhaler use data and patient self-assessments from the App. The patient has no interaction with the dashboard. Teva personnel will have no access to the dashboard.

5.1.3. Reference Investigational Medicinal Product or Device

Not applicable.

5.1.4. Placebo Investigational Medicinal Product or Device

Not applicable.

Table 4: Investigational Medicinal Products Used in the Study

IMP name	Test IMP	Placebo IMP	Reference IMP
Trade name	Albuterol eMDPI	None	None
Formulation	Oral inhalation powder	NA	NA
Unit dose strength	117 mcg of albuterol sulfate (equivalent to 97 mcg of albuterol base) from the device reservoir to provide a delivered dose of 108 mcg of albuterol sulfate (equivalent to 90 mcg of albuterol base)	NA	NA
Route of administration	Oral inhalation	NA	NA
Dosing instructions	1 to 2 oral inhalations every 4 to 6 hours, as needed	NA	NA
Packaging	NA	NA	NA
Manufacturer	Teva Pharmaceutical Industries, Ltd. Jerusalem, Israel, or Teva Pharmaceuticals Ireland, Waterford, Ireland	NA	NA

eMDPI=multidose dry powder inhaler with integrated electronic module; IMP=investigational medicinal product; NA=not applicable.

5.2. Preparation, Handling, Labeling, Storage, and Accountability for IMPs

5.2.1. Storage and Security

The investigator or designee must confirm that appropriate temperature conditions have been maintained for all IMP received, and any discrepancies are reported and resolved before use of the IMP.

The IMP must be stored at room temperature (15°C to 25°C [59°F to 77°F]) and not exposed to extreme heat, cold, or humidity. The investigational center personnel are responsible for acknowledging receipt of the IMP using a Randomization and Trial Supply Management (RTSM) system.

5.2.2. Labeling

Supplies of IMP will be labeled according to the current International Council for Harmonisation (ICH) guidelines on Good Clinical Practice (GCP) and Good Manufacturing Practice and will include any locally required statements.

5.2.3. Accountability

Each IMP shipment will include a packing slip listing the contents of the shipment and any applicable forms.

The investigator is responsible for ensuring that deliveries of IMP for initial distribution to patients and other study materials from the sponsor are correctly received, recorded, handled, and safely and properly stored in accordance with national and local regulations, and used in accordance with this protocol.

Only patients enrolled in the study may receive IMP, and only authorized personnel at the investigational center may supply or administer IMP. All IMP must be stored in a secure, environmentally controlled, and monitored (manual or automated) area in accordance with the labeled storage conditions or appropriate instructions with access limited to the investigator and authorized personnel at the investigational center. The investigator (or designee) will instruct the patient to store the IMP according to the instructions on the label, if applicable; or will give instructions in an appropriate form. Patients will be instructed to return all IMP (empty, partially used, and unused inhalers) to the investigational center at end of treatment (Visit 2) or at the ET visit.

The investigator, institution, or the head of the medical institution (where applicable) is responsible for IMP accountability, reconciliation, and record maintenance (ie, receipt, reconciliation, and final disposition records). Patients will return all inhalers at the end of the study to the investigational center for reconciliation.

A record of IMP accountability (ie, IMP and other study materials received, used, retained, and returned) must be prepared and signed by the principal investigator or designee, with an account given for any discrepancies. All empty, partially used, and unused inhalers will be collected at the end of the study and will be returned to the sponsor or designee per sponsor instructions.

Further guidance and information are provided in the Study Pharmacy Manual.

5.3. Justification for Investigational Medicinal Product

5.3.1. Justification for Dose of Test Investigational Medicinal Product

The prescribed dose of Albuterol eMDPI (now US FDA approved as PROAIR DIGIHALER) used in this study (ie, 90 mcg, 1 to 2 inhalations every 4 to 6 hours, as needed) was selected based on the prescribing information for PROAIR DIGIHALER.

PROAIR DIGIHALER is indicated for the management of asthma and relief of acute symptoms of asthma in adults and children 4 years and older, and for the prevention of EIB. For the relief of acute asthma symptoms, PROAIR DIGIHALER is recommended at a dosage of 2 inhalations (ie, 180 mcg of albuterol base ex-mouthpiece) repeated every 4 to 6 hours, as needed. More frequent administration or a larger number of inhalations is not recommended. In some patients, 1 inhalation every 4 hours may be sufficient. The recommended dosage for PROAIR DIGIHALER for the prevention of EIB in adults and children 4 years of age or older is 2 inhalations 15 to 30 minutes before exercise. To date, the overall results of clinical studies provide robust and consistent evidence that PROAIR DIGIHALER is effective for the treatment or prevention of bronchospasm in adult and adolescent patients with obstructive airway disease.

5.4. Treatment After the End of the Study

No treatment is planned by the sponsor after the end of the study. Patients are advised to consult with their primary physician for treatment.

5.5. Restrictions

There are no additional restrictions beyond the inclusion and exclusion criteria in this study and the prohibited medication noted in Section [5.6](#).

5.6. Prior and Concomitant Medication or Therapy

Any concomitant medication a patient is taking at screening and up to the final visit will be recorded on the CRF. Trade name and international nonproprietary name (if available), indication, dose, and start and end dates of the administered medication will be recorded. The sponsor will encode all medication according to the World Health Organization (WHO) drug dictionary (WHO Drug).

The use of other SABA products, by the DS group, is prohibited during this study except for the use of nebulized albuterol, as needed, in the ED for an acute exacerbation of asthma.

At the end of treatment visit (Visit 2), patients will be asked whether they have taken any medications (other than IMP), including over-the-counter medications, vitamins, or herbal or nutritional supplements, since the previous visit.

Concomitant medication and treatment will be recorded through the final visit.

5.7. Procedures for Monitoring Patient Compliance

Since the IMP is a rescue medication, it will be used on an “as needed” basis. The investigator will be responsible for dispensing IMP, training patients on the correct use of IMP, return of IMP, and IMP accountability records will be completed.

If the investigator or the sponsor determines that the patient is not in compliance with the study protocol, the investigator and the sponsor should determine whether the patient should be withdrawn from the study.

Exposure to IMP will be assessed as required.

5.8. Randomization and Blinding

This is an open-label study and patients will be randomly assigned to the DS group or CC group in a 1:1 ratio stratified by investigational center, using a RTSM system. Since this an open-label study, blinding is not applicable.

5.9. Data Monitoring Committee

There will be no Data Monitoring Committee for this study.

6. ASSESSMENT OF EFFICACY

The efficacy of the drug product will not be evaluated in this study. The focus of this study is the engagement of the patient with the Albuterol eMDPI DS.

6.1. Assessments of Patient-Reported Outcomes

6.1.1. Asthma Control Test

The ACT is a simple, patient-completed tool used for the assessment of overall asthma control. The 5 items included in the ACT assess daytime and nighttime asthma symptoms, use of rescue medication, and impact of asthma on daily functioning. Each item in the ACT is scored on a 5-point scale, with summation of all items providing scores ranging from 5 to 25. The scores span the continuum of poor control of asthma (score of 5) to complete control of asthma (score of 25), with a cutoff score of 19 and below indicating patients with poorly controlled asthma ([Schatz et al 2006](#)).

The ACT should be the first questionnaire completed by all patients during a study visit (the second should be the BMQ, and the third the BIPQ (both by patients 18 years of age or older), and should precede any discussion between the patient and investigational center personnel. The self-administered version of the ACT will be answered by the patients at the investigational center at Visit 1, Visit 2, or at the Early Termination (ET) visit. The investigators and personnel will be provided with detailed instructions for administering the ACT in order to achieve maximum compliance in a clinical study environment and maximum data quality. Caregivers or investigational center personnel will not be allowed to interfere or communicate with the patient completing the questionnaire beyond restating the question(s) on the questionnaire exactly as they have been written. After completion of the ACT, investigational center personnel will check the questionnaires for completeness and legibility. Detailed instructions for administering, scoring, and analyzing the ACT are provided in the Statistical Analysis Plan.

6.1.2. Beliefs about Medicines Questionnaire

The BMQ is used to assess cognitive representations of medicine ([Horne, Weinman, and Hankins 1999](#)). The BMQ-Specific (BMQ-S11) is an 11-item questionnaire that assesses representation of medication prescribed for personal use and the BMQ-General assesses beliefs about medicines in general. For the purposes of this study, the BMQ-S11 will be completed by patients, 18 years of age or older, at the investigational center at Visit 1, Visit 2, or at the ET visit. The BMQ should be the second questionnaire completed during a study visit following the ACT.

6.1.3. Brief Illness Perception Questionnaire

The BIPQ is a 9-item questionnaire designed to rapidly assess cognitive and emotional representations of illness ([Broadbent et al 2006](#)). The BIPQ uses a single-item scale approach to assess perception on a 0-10 response scale. It is developed by forming one question that best summarizes the items contained in each subscale of the Illness Perception Questionnaire-Revised which has over 80 items. The BIPQ comprises 5 items on cognitive representation of illness perception: consequences, timeline, personal control, treatment control, and identity. There are 2 items on emotional representation: concern and emotions; one item is on illness

comprehensibility. The last item is on perceived cause of illness, in which respondents list the 3 most important causal factors in their illness. For this questionnaire, the general word 'illness' can be replaced by the name of a particular illness such as asthma. The word 'treatment' in the treatment control item can be replaced by a particular treatment such as 'surgery' or 'physiotherapy' (Broadbent et al 2006). The discriminant validity of the questionnaire is supported by its ability to distinguish between different illnesses, namely asthma, diabetes, colds, myocardial infarct prior to discharge, and pre-diagnosis chest pain patients waiting stress exercise testing. The BIPQ will be answered by the patients, 18 years of age or older, at the investigational center at Visit 1, Visit 2, or at the ET visit. The BIPQ should be the third questionnaire completed during a study visit following the BMQ.

6.1.4. System Usability Questionnaire

The SUS will be used to explore device acceptability and usability for patients in the DS group. It is a 10-question tool that provides a composite measure of the overall usability of the system being studied. It has been used extensively across many industries, patient types, and technologies, and has been used in studies of patients with asthma and COPD (Brooke 1996). The SUS will be answered by patients in the DS group, 18 years of age or older, at Visit 2, or at the ET visit. The SUS will be completed after all other questionnaires.

An SUS regarding the use of the dashboard will be completed by investigational center personnel at the end of the study.

7. ASSESSMENT OF SAFETY

In this study, safety will be assessed by qualified study personnel by evaluating reported adverse events, adverse device effects, vital signs measurements, and use of concomitant medications.

Adverse events are categorized by ICH guidelines, and adverse device effects are categorized and classified according to International Organization for Standardization (ISO) standard 14155:2011(E).

Device deficiencies that are not associated with an adverse event as well as those that have the potential to cause a serious adverse event are covered in [Appendix F](#).

7.1. Adverse Events

7.1.1. Definition of an Adverse Event

An adverse event is any untoward medical occurrence, unintended disease or injury, or untoward clinical signs (including abnormal laboratory findings) in patients or clinical investigation subjects, users or other persons, whether or not related (causal relationship) to the pharmaceutical product (treatment), investigational medical device, or comparator. This definition includes events related to the procedures involved. For users or other persons, this definition is restricted to events related to investigational medical devices.

An adverse event can, therefore, be any unfavorable and unintended physical sign, symptom, or laboratory parameter that develops or worsens in severity during the course of this study, or significant worsening of the disease under study or of any concurrent disease. A new condition or the worsening of a pre-existing condition will be considered an adverse event. Stable chronic conditions (such as arthritis) that are present before study entry and do not worsen during this study will not be considered adverse events.

Accordingly, an adverse event can include any of the following:

- intercurrent illnesses
- physical injuries
- events possibly related to concomitant medication
- significant worsening (change in nature, severity, or frequency) of the disease under study or other pre-existing conditions
- drug/drug, drug/device, or device/device interactions
- events occurring during diagnostic procedures of this study

Worsening of asthma that occurs during the study that is not typical of the patient's daily symptoms or leads to the patient's discontinuation will be considered an adverse event.

A CAE will be defined by 1 of the following: 1) in-patient hospitalization because of asthma, 2) emergency treatment because of asthma, 3) a worsening of asthma symptoms leading to the use of prednisone or systemic corticosteroids for 3 days or more, or 4) a reduction in FEV₁ of 20% or greater. Patients will be instructed to contact the study investigational center in the event of a CAE.

All CAE events require documentation by the investigator in the CAE Page in the CRF, as well as in the adverse event CRF. All evaluations entered into the CAE Page require the investigational center to obtain source documentation of all CAEs that occur during the treatment period to confirm the accuracy of the information obtained from the patient. Any CAE that meets serious adverse event criteria will be reported as a serious adverse event (Section 7.1.5.1).

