3. STUDY DESIGN

3.1. General Study Design and Study Schematic Diagram

This is a 12-week treatment, multicenter, open-label, randomized, parallel group comparison feasibility study to evaluate the effectiveness of the Albuterol eMDPI DS, including inhaler, App, DHP (Cloud solution), and dashboard, to optimize outcomes in patients at least 13 years of age or older with asthma.

The study will consist of a screening/baseline visit (Visit 1), a 12-week open-label treatment period with Visit 2, and a follow-up telephone call (2 weeks following treatment completion).

Patients with suboptimal asthma control will be enrolled in the study and randomized in a 1:1 ratio to 1 of 2 parallel groups stratified by investigational center: DS group patients utilizing the Albuterol eMDPI DS, including inhaler, App, DHP (Cloud solution), and dashboard, and CC group patients who will be treated with their standard of care albuterol-administering rescue inhalers and will not use the DS during the treatment period. Similar data will be collected regarding outcomes for the CC group: ACT after 12 to 14 weeks, BMQ and BIPQ responses, and the frequency of CAEs.

All patients will have a screening/baseline visit (Visit 1), at which they will be asked if they use a smart device and use different applications on their smart devices. A baseline ACT score for all patients, and BMQ and BIPQ responses for patients 18 years of age or older, will be collected. Once randomized, patients in the DS group will be trained on the use of the Albuterol eMDPI DS (including instructions on how to use both the eMDPI and the App) and, upon demonstrating competency, will receive 2 Albuterol eMDPI devices for use as rescue bronchodilators to replace their rescue treatment during the study. Additional Albuterol eMDPI devices may be supplied during the treatment period, based on patients' needs. Patients in the CC group will be reimbursed or given a voucher to use to purchase their existing rescue medications.

Investigational centers will also receive similar instruction regarding features of the App, as well as features of the associated dashboard, which mirrors the digital information obtained from the eMDPI and App, including frequency and times of SABA rescue use and associated inspiratory flow parameters measured by the eMDPI with each inhalation.

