7.7. Vital Signs

Vital signs (blood pressure [systolic/diastolic], pulse rate, and respiratory rate) will be measured at the time points detailed in [Table 3](#). All vital signs results outside of the reference ranges will be judged by the investigator as belonging to 1 of the following categories:

- abnormal and not clinically significant

- abnormal and clinically significant

Before blood pressure and pulse are measured, the patient must rest in a seated position for at least 5 minutes. The same position and arm should be used each time vital signs are measured for a given patient. For any abnormal vital sign value, the measurement should be repeated as soon as possible. Any vital sign value that is judged by the investigator as clinically significant will be recorded both on the source documentation and the CRF as an adverse event, and monitored as described in Section 7.1.2.

In addition, potentially clinically significant values will be predefined by the sponsor for selected vital sign parameters and will be detailed in the Statistical Analysis Plan.

7.8. **Electrocardiography**

No electrocardiogram measurements are scheduled to be performed during this study.

**8. ASSESSMENT OF PHARMACOKINETICS /
PHARMACODYNAMICS / BIOMARKERS /
PHARMACOGENOMICS/ IMMUNOGENICITY/ANCILLARY
STUDIES**

Pharmacokinetic, pharmacodynamic, biomarker, pharmacogenomics, immunogenicity, or other ancillary parameters will not be evaluated in this study.

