A Clinically Driven Assessment, which can either be via telephone or an on-site visit, may be performed at any time during the study at the patient's request and as deemed necessary by the investigator. For DS patients, the investigator will have access to information from the Albuterol eMDPI on the patient's SABA use and inhalation technique through the dashboard. If the investigator meets with or calls the patient as a result of an interaction with the dashboard, this will be captured as a Clinically Driven Assessment.

The date and reason for the Clinically Driven Assessment (eg, treatment step up, treatment step down, adherence discussion, treatment for an asthma exacerbation, or other clinical encounters generated by the data from the Albuterol eMDPI), as well as any other data obtained from procedures and assessments, will be recorded in the patient's source documents and the case report form (CRF) for patients in both groups, during the 12-week treatment period.

The following procedures and assessments will be performed at a Clinically Driven Assessment:

- conduct adverse events and adverse device effects inquiry
- conduct concomitant medication inquiry
- iHCP asks Asthma Management questions
- dispense Albuterol eMDPI, as needed (if on-site and necessary)

Other procedures and assessments may be performed at the discretion of the investigator.

5. Procedures for an Unscheduled Investigational Medicinal Product Dispensing Visit

The following procedures and assessments will be performed at an unscheduled IMP dispensing visit:

- conduct adverse events and adverse device effects inquiry
- conduct concomitant medication inquiry
- perform Albuterol eMDPI collection and accountability
- dispense test investigational medicinal product (IMP) to DS group patients

6. Procedures for Follow-up Telephone Call (Day 98 + 7 days)

The following procedures and assessments will be performed at the follow-up telephone call:

- conduct adverse events and adverse device effects inquiry

- conduct concomitant medication inquiry
- for DS group patients, confirm that the patient has returned to previous asthma treatment

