8.4. Adverse Events

All adverse events will be coded using the MedDRA. Adverse events occurring on or after the treatment start date will be included in the summary tables while all of the adverse events will be listed in data listings.

A summary will be presented for adverse events in the following categories: all adverse events, adverse events determined by the investigator to be related to study drug, severe adverse events, serious adverse events, adverse events leading to withdrawal from the study, non-serious adverse events, device-related adverse events (DS group only), asthma related adverse events, and CAE related adverse events. The incidence of patients with an adverse event in each category will be summarized using descriptive statistics.

Summaries will be presented for all adverse events (overall and by severity), adverse events determined by the investigator to be related to study drug (overall and by severity), serious adverse events, adverse events leading to withdrawal from the study, non-serious adverse events, and device-related adverse events (DS group only).

The incidence of adverse events will be summarized using descriptive statistics by SOC and preferred term (all AEs overall will also be presented by just preferred term category). Patients are counted only once in each SOC category, and only once in each preferred term category. For the summaries by severity, patients are counted at the greatest severity. Adverse events with the missing flag indicating serious will be excluded from the summary of serious adverse events but included in the summary of non-serious adverse events.

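### The FEV1 criterion for a clinical asthma exacerbation has no planned measurement and no reference value, so FEV1-only events may be detected unevenly between the arms

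*Protocol*

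**What the plan says.** Protocol 7.1.1 lists four criteria, any one of which makes a CAE: hospitalization for asthma, emergency treatment for asthma, "a worsening of asthma symptoms leading to the use of prednisone or systemic corticosteroids for 3 days or more", and "a reduction in FEV₁ of 20% or greater". The fourth stands alone, with no reference value, timing or method. The stated route for finding events is that "Patients will be instructed to contact the study investigational center in the event of a CAE".

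Lung function is not among the planned assessments. Protocol 7 says safety is assessed by "evaluating reported adverse events, adverse device effects, vital signs measurements, and use of concomitant medications". Protocol 7.7 gives the content of the vital signs: "Vital signs (blood pressure [systolic/diastolic], pulse rate, and respiratory rate) will be measured". Neither Table 3 nor Appendix B lists spirometry at any visit or call. SAP 8.3 covers flow recorded by the inhaler, not FEV1. The one opening is in Appendix B, under Clinically Driven Assessments: "Other procedures and assessments may be performed at the discretion of the investigator".

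CAE frequency is nevertheless outcome data. Protocol 3.1 names, for the concurrent control (CC) group as for DS, "ACT after 12 to 14 weeks, BMQ and BIPQ responses, and the frequency of CAEs". SAP 8.4 includes "asthma related adverse events, and CAE related adverse events" among its summary categories, and SAP 8.1 has safety summaries presented by treatment group.

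**The concern.** A criterion that nobody is scheduled to measure still counts toward an event frequency shown by arm. If the chance of having spirometry differs between arms, the number of FEV1-only events will differ too, even when the true risk is the same. The trial is open-label, and the intervention gives staff additional reasons to contact DS patients. At stake is a reader's interpretation of the by-arm CAE line: a modest excess in DS could reflect closer observation rather than worse asthma, and the planned table would give no means of telling the two apart.

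**Working it through.** The documents state no CAE rate, so there is no figure of the plan to reproduce. The check sets the passages side by side and then illustrates the mechanism.

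**1. What each criterion needs**

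| Criterion | How it comes to light | Needs spirometry? |
|---|---|---|
| 1. Hospitalization | Patient report, source records | No |
| 2. Emergency treatment | Patient report, source records | No |
| 3. Systemic corticosteroid, 3 days or more | Patient report, medication record | No |
| 4. FEV1 fall of at least 20% | A current FEV1 and an earlier one | Yes, both unscheduled |

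A patient can recognize the first three and call the center, but not an FEV1 fall that nobody measured. The source-documentation rule in Protocol 7.1.1 verifies CAEs already reported; it cannot reveal unmeasured falls.

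**2. Routes to contact** (Protocol 3.1, Table 3, Appendix B)

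- Both arms: Visit 1, Visit 2, one follow-up call, patient-initiated contact for a CAE, and Clinically Driven Assessments by clinical judgment, by telephone or on site.
- DS only: dashboard review at least weekly, contact arising from the dashboard (recorded as a Clinically Driven Assessment), and unscheduled dispensing visits that include an adverse event inquiry.

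DS has more routes, but no number of contacts is set for either arm.

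**3. Illustration** (every rate here is an assumption)

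Let r be the share of patients with a CAE by criteria 1 to 3, q the share with an FEV1 fall only, and s the chance that such a fall is measured. The observed CAE share is r + q × s. Take r and q as equal in both arms, so that there is no true difference.

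With r = 5%, q = 6% and s = 0.20 in CC:

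- CC: 0.05 + 0.06 × 0.20 = 0.062.
- DS, s = 0.40: 0.05 + 0.06 × 0.40 = 0.074; ratio 0.074 / 0.062 = 1.19.
- DS, s = 0.30: 0.068 / 0.062 = 1.10.
- DS, s = 0.50: 0.080 / 0.062 = 1.29.

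With 150 patients per arm (Protocol 9.1), the middle case is 150 × 0.074 = 11.1 against 150 × 0.062 = 9.3 patients.

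Wider grid, with s = 0.20 in CC, r of 5% to 10%, q of 5% to 20% and s in DS of 0.30 to 0.60:

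- Smallest ratio: (0.10 + 0.05 × 0.30) / (0.10 + 0.05 × 0.20) = 0.115 / 0.110 = 1.05, or 150 × 0.005 = 0.75 extra DS patients.
- Largest ratio: (0.05 + 0.20 × 0.60) / (0.05 + 0.20 × 0.20) = 0.170 / 0.090 = 1.89, or 150 × 0.080 = 12 extra DS patients.

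If FEV1-only falls are rare (r = 5%, q = 1%, s = 0.40 against 0.20), the result is 0.054 / 0.052 = 1.04. With equal s, the ratio is 1.00.

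**The case against.** The strongest reply is that little here is likely to move a number. A Clinically Driven Assessment may be a telephone call, which yields no FEV1. Dispensing visits have their own procedure list without lung function. Two 200-actuation inhalers at Visit 1 cover 400 / 84 = 4.8 inhalations a day, so resupply visits need not be common. Earlier chart values or outside spirometry could supply a reference, and discretionary spirometry at Visit 2 is not ruled out. The CAE line is descriptive and untested. In the illustration's middle case, the gap of 1.2 points is well below its standard error of about 2.9 points, √(0.074 × 0.926/150 + 0.062 × 0.938/150). All of this stands, and it limits the point to a modest one. It does not supply a planned measurement or a defined reference.

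A reader might infer two stronger things. The first is that contact is more frequent in DS by design. The documents do not say so: scheduled contacts are identical, Clinically Driven Assessments are open to both arms, and no clinical action is mandated. DS has more possible triggers, which makes more contact likely but not certain. The second is that the between-arm CAE comparison cannot be interpreted at all. That does not follow either, since criteria 1 to 3 need no spirometry.

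It is also fair to object that a count on criteria 1 to 3 does not remove every difference in observation. Criterion 3 turns on a prescribing decision, and dashboard data are meant to inform asthma management. That stands as a limit of the fix.

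**Conclusion.** The point holds as a small, inexpensive improvement to a descriptive safety summary. As written, FEV1-only CAEs enter the count only where someone happens to measure FEV1, against a reference that the plan leaves open. If DS contact is higher and some of it leads to spirometry, the distortion runs against DS. Its size cannot be derived from the documents: the ratios of 1.04 to 1.89 rest wholly on assumed event rates and detection chances, and the lower end would hardly be noticed.

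The ACT responder endpoint, its stated power of 0.77 and its type 1 error are untouched, and CAE is not part of secondary endpoints #1 to #4. The exploratory endpoints are redacted, so no weight is placed on a possible CAE endpoint there.

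**What to change.** Keep the protocol definition for safety reporting. In SAP 8.4:

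- tabulate CAEs by qualifying criterion and arm;
- use criteria 1 to 3 for the between-arm CAE frequency;
- list FEV1-only CAEs separately by arm, with the reference value used for each and the number of patients in each arm who had any FEV1 reading;
- report the number of unscheduled contacts per arm, so that a reader can judge how far observation differed.

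Confirm that the CAE page of the case report form captures the qualifying criterion. The page is not in the documents and may already do so; if not, one field is needed.

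The cost is SAP wording before database lock, plus that field if it is missing. The downsides are that a few FEV1-only events leave the comparative count, and that the remaining count still depends partly on contact and treatment decisions through criterion 3.
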